EMG/EEG Lab Visits. Task 1: Startle response to threat. Consistent with prior studies^{54,55}, participants will first complete a brief habituation task to prevent early exaggerated startle responding, during which a series of acoustic startle probes will be administered. For the threat task itself, a brief, mild electric shock will be used to elicit aversive responding. Importantly, the current shock equipment and shock protocol has previously been used in our laboratory. Prior to the task, shock electrodes will be placed on the participants' left wrist, followed by a shock work-up procedure in which they will receive increasing levels of shock intensity (max. = 5 mA) until they reach a level that they describe as feeling "highly annoying but not painful." Shock level will be determined ideographically to ensure equality in perceived shock aversiveness. The task itself includes three within-subjects conditions – no shock (N), predictable shock (P), and unpredictable shock (U). Text at the bottom of the screen informs participants of the current condition. Conditions last 145-s, during which a 4-s visual countdown (CD) is presented six times. The interstimulus intervals (ISIs) range from 15 to 21-s during which only the text of the condition is on the screen. No shocks are delivered during the N condition. A shock is delivered every time the CD reaches 1 during the P condition. Shocks are delivered at random during the U condition. Startle probes are administered during both the CD and ISI. Each condition is presented two times in a randomized order. Participants receive 24 shocks (12 in P; 12 in U) and 60 startle probes (20/condition). This task will be conducted during all three EMG visits, including the Acute Drug Challenge Visit.

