Administration Timing. Peak plasma concentration for suvorexant is 2 hours post-ingestion. Therefore, participants will receive the drug (or placebo) at the CRC upon arrival. After 1.5 hours (90 minutes post ingestion), participants will be escorted to the laboratory for EMG/EEG testing. Laboratory assessments will occur during peak concentration, ~2 hours post-ingestion.

Self-Report Assessments During Acute Drug Challenge. Throughout the Acute Drug Challenge Visit standardized questionnaires will be used to assess mood states and subjective drug effects: (1) Karolinska Sleepiness Scale (KSS)⁶²; (2) Anxiety Visual Analog Scales (VAS)⁶³; and (3) Drug Effects Questionnaire (DEQ)⁶⁴; and Profile of Mood

States (POMS)⁶⁵. The KSS, VAS and DEQ will be collected immediately before capsule ingestion (Time 0), and approximately 30, 60, 90, 120, 150, 180, and 210, and 240 minutes afterwards. The POMS will be completed immediately prior to capsule ingestion (Time 0), and approximately 60 minutes, 120 minutes, and 240 minutes afterwards.

Vitals Signs Measurements During Acute Drug Challenge. Physiologic measures will be collected throughout the study visit: (1) Blood Oxygen (O₂) Saturation; (2) Heart Rate and (3) Blood Pressure will be taken before capsule ingestion (Time 0), and approximately 30, 60, 90, 120, 150, 180, and 210, and 240 minutes afterwards. Measurements will be performed at the CRC or in the PI's lab using portable blood pressure and finger oximeter. Measurements will be obtained using a finger oximeter and portable blood pressure cuff. Any participant who experiences excessive drowsiness, allergy symptoms, and/or adverse drug reactions will be assessed by the CRC and study physician and immediately withdrawn from the study as a safety measure.

Drug Trial and Monitoring. At the end of the acute challenge, subjects will be provided the rest of their prescription (SUV or placebo) in blister packaging, prepared by OSU IDS. The blister packaging will be labeled with each date of the protocol. Subjects will be directed to ingest one pill each night, as they get into bed (~30 mins prior to sleep time) to mitigate drowsiness, consistent with SUV's prescription.

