10.0 Quality Control and Quality Assurance

- Please see bullet below for description on how startle and fMRI data is evaluated for adherence with the protocol. As noted above, all self-report data will be double entered, checked for discrepancies, and cleaned. Analyses will assume that ‘missingness’ occurred at random, with data imputed when necessary. Type 1 error rates will be adjusted using Bonferroni corrections.
- The PI of the study and her research staff are responsible for the monitoring of the research and the evaluation of the data quality. After each session data is transferred to the lab storage drive. The data is closely reviewed to ensure its quality and that nothing is missing.
- Both startle and fMRI data are processed using automated scripts; however, the PI and study staff examine each blink file by hand to ensure acceptability and high-quality data.

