12.0 Statistical Considerations

13.0 Aim 1. Does a single dose of SUV decrease reactivity to U-threat? Hypothesis

1: Relative to PBO, SUV will acutely dampen startle reactivity to U-threat, but not P-threat. We will conduct a multilevel mixed model with startle magnitude as the dependent variable. Startle to U-threat and P-threat will be included as a within-subjects factor, to test for specific changes in U-threat. Time (baseline vs. acute challenge) and treatment arm (SUV vs. PBO) will be included as within-subjects and between-subjects factors, respectively, and we expect a time x treatment arm x task condition interaction on startle. Models will include a random effect for participant.

14.0 Aim 2. Does daily use of SUV decrease reactivity to U-threat? Hypothesis 2a:

4-weeks of SUV will result in greater reductions in reactivity to U-threat compared with PBO, and these changes will be specific to U-threat. Hypothesis 2b: SUV-related change in U-threat reactivity will be greatest amongst those with higher baseline U-threat reactivity. Exploratory Analysis: SUV will similarly result in decreases in aINS and dACC reactivity and connectivity during U-threat relative to PBO, and brain change will correlate with startle change. For H2a, we will conduct a multilevel mixed model that is nearly identical to the model described for H1. However, the time variable will be modeled as baseline vs. post-treatment. For H2b,

we will include baseline startle to U-threat as a predictor in our model and test for a baseline startle by treatment arm interaction. Lastly, for our exploratory fMRI analyses, we will first extract activation and functional connectivity parameter estimates from anatomical aINS and dACC during U-threat (and P-threat) > No-threat contrast maps. fMRI variables will be tested as dependent variables in the model used for H2a. Magnitude of brain change will be directly correlated with magnitude of startle change.

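### H2a leaves out the acute-visit startle: if later loss depends on that value and the arms differ in acute response or dropout, the 4-week contrast is modestly biased; a three-visit model helps only with visit-by-condition covariance

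*Combined protocol and SAP*

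**What the plan says.** Section 12.0 sets out two separate two-visit models.

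- **H1 (Aim 1, numbered 13.0):** "Time (baseline vs. acute challenge) and treatment arm (SUV vs. PBO) will be included as within-subjects and between-subjects factors". The test is the three-way term: "we expect a time x treatment arm x task condition interaction on startle", where condition is U-threat against P-threat. The only covariance statement is "Models will include a random effect for participant".
- **H2a (Aim 2, numbered 14.0):** the model is "nearly identical to the model described for H1", with this difference: "However, the time variable will be modeled as baseline vs. post-treatment".

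The acute value exists. Section 6.0 says of the startle task: "This task will be conducted during all three EMG visits, including the Acute Drug Challenge Visit".

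Loss around the acute visit is foreseen. In section 6.0, under the vital-signs measurements for that visit: "Any participant who experiences excessive drowsiness, allergy symptoms, and/or adverse drug reactions will be assessed by the CRC and study physician and immediately withdrawn".

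On missing data, section 10.0 says missingness is taken to have "occurred at random, with data imputed when necessary". That sentence directly follows one on double entry of self-report data, and its twin in section 6.0 stands under self-report processing. No imputation model, auxiliary variable, dropout rate or sensitivity analysis is given for startle.

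**The concern.** A participant lost after the acute visit contributes only a baseline value to H2a. Any claim that the missing 4-week value is missing at random must then hold without reference to the acute value. That value was measured under study drug about four weeks before the missing one, on the same task, and is likely to predict it. If people leave according to how their startle responded to the first dose, those still present at post-treatment are a selected group, and the selection may differ by arm.

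H2a is the 4-week target-engagement result, and section 1.0 says the findings will be used to power a larger trial. A shift in this estimate would carry into that calculation.

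**Working it through.** **1. The plan's own figure.** The sample-size paragraph gives 91% power at 40 per arm for a medium to large effect, with no number, SD, alpha or sidedness. It cannot be reproduced from stated inputs. With a two-sided 0.05 t-test, 91% needs d = 0.747. The first simulation below uses 0.74 (90.5% by t-test, 91.1% by normal approximation).

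**2. Dropout.** Approval is sought for 120 against 80 needed, a margin of 40/120 = 33%, but this pools screen failures, dropouts and withdrawals. Loss after the acute visit is not stated. All loss rates, slopes and correlations below are assumptions.

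**3. What a participant random intercept does to the three-way test.** Write startle for participant i, visit v, condition c as Y = mean(arm, v, c) + b_i + e_ivc. Then

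D_iv = Y_ivU − Y_ivP = mean difference + (e_ivU − e_ivP).

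The intercept b_i cancels, so the model treats D at different visits as uncorrelated. When U and P are observed or missing together, the H2a three-way estimate is the arm difference in mean D among those seen post-treatment, minus the arm difference in mean D at baseline. Neither the baseline nor the acute value adjusts for who has left. Numerically, over 200 simulated trials of 40 per arm, the two-visit and three-visit random-intercept estimates differed by at most 6e-16.

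**4. How much acute information baseline leaves unused on U alone.** With all visit correlations at 0.6, the coefficient of post on acute, given baseline, is (0.6 − 0.6×0.6)/(1 − 0.6²) = 0.24/0.64 = 0.375.

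**5. Large-sample bias.** Simulation of 20,000 per arm, 10 runs; true effect on U −0.74 SD at post-treatment, and at the acute visit unless noted; loss logistic in acute U startle. RI = participant random intercept; UN = unstructured. Visit correlations are 0.6, except in the last row (adjacent visits 0.7, baseline-post 0.4). Monte Carlo error is at most 0.004. Positive values mean that the effect is shrunk.

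| Dependence of loss on acute U startle | Loss SUV/placebo | U alone: 2-visit RI | 3-visit RI | 3-visit UN | Three-way: 2-visit RI | 3-visit RI | 2-visit UN | 3-visit UN |
|---|---|---|---|---|---|---|---|---|
| None | 20/20% | 0.002 | 0.002 | 0.002 | 0.001 | 0.001 | 0.002 | 0.002 |
| Same rule in both arms, high startle leaves | 15/25% | 0.022 | 0.002 | 0.002 | 0.018 | 0.018 | 0.007 | −0.001 |
| Same rule, no acute drug effect | 20/20% | 0.003 | 0.002 | 0.002 | 0.005 | 0.005 | 0.005 | 0.005 |
| SUV only, low startle leaves | 22/18% | 0.048 | 0.002 | 0.003 | 0.046 | 0.046 | 0.019 | 0.001 |
| SUV only, high startle leaves | 22/18% | −0.048 | −0.003 | −0.003 | −0.051 | −0.051 | −0.025 | −0.006 |
| SUV only, steep slope | 34/26% | −0.186 | −0.020 | 0.003 | −0.116 | −0.116 | −0.074 | 0.003 |

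The steep row is a stress case: 0.116/0.74 = 16% on the three-way contrast and 0.186/0.74 = 25% on U alone.

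**6. Trial-size bias.** Simulation of 40 per arm; true effects −0.60 SD (acute) and −0.50 SD (post-treatment); visit correlations 0.5-0.8; loss about 20-28% on SUV and 10-16% on placebo.

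| Dependence of loss on acute fall | 2-visit bias, U alone | 2-visit bias, U minus P | 3-visit UN |
|---|---|---|---|
| SUV only | 0.04-0.13 | 0.01-0.05 | at most 0.01 |
| One rule in both arms | 0.01-0.05 | 0.005-0.02 | at most 0.01 |

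**7. Against sampling error.** With 32 per arm and r = 0.6, the standard error of the arm difference in change on U is √[2(1 − 0.6)] × √(2/32) = 0.894 × 0.25 = 0.22. A three-way bias of 0.05 is about a quarter of a standard error; 0.13 on U alone is about 0.6 of one.

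**8. Precision.** For a single outcome with 15% random loss in both arms, the three-visit standard error is 1.5-3% smaller, equivalent to 1/0.985² − 1 = 3% to 1/0.97² − 1 = 6% more participants. Under one loss rule in both arms, root-mean-square error improved by only 0-2%.

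**The case against.** The strongest reply is that the mechanism is assumed. The withdrawal rule names drowsiness, allergy symptoms and adverse reactions, not low startle, and nothing in the documents ties these to the startle response. Section 6.0 reports pilot change in U-threat reactivity without adverse reactions. The rule applies to any participant under double blind, so a one-arm mechanism is the less natural case, and with a common rule the three-way bias is 0.02 SD or less in these runs. Dosing precedes the EMG by about two hours, so someone withdrawn early has no acute startle to use. All of this stands, and it limits the size of the point.

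Three stronger readings are tempting, and the documents do not support them.

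- *That the H2a estimate is biased as planned.* It is exposed to bias under conditions. Where the loss rule was the same in both arms and the drug had no acute effect, the bias was within simulation noise.
- *That any three-visit model cures it.* Under the only covariance term that the plan names, read as a random intercept, adding the visit changes nothing in the three-way test. It removes most of the bias for U alone only.
- *That the plan has declared startle missing at random.* The sentence sits with self-report handling, so applying it to startle is inference.

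What does not stand is any suggestion that the gap is closed elsewhere. No passage brings acute startle into the 4-week analysis, by model or by imputation.

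**Conclusion.** The structural point holds: H2a sets aside an informative measurement already in hand. The harm is conditional. It needs loss that depends on acute startle, together with an arm difference in acute response or in dropout mechanism; H1, if true, supplies the former.

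Under the trial-size assumptions the bias is about 0.01-0.05 SD on the contrast that H2a names and 0.01-0.13 SD on U alone, mostly well below one standard error. The larger stress-case values need about 30% loss and a steep one-arm mechanism. The direction is not fixed: the table shows both shrinkage and exaggeration. A reader might infer that the main gain is precision; it is not, since that gain is small.

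Severity is minor to moderate. Confidence is high in the structure and low in any particular percentage, because dropout, correlations and mechanism are all assumed.

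**What to change.** Replace the two models under Aims 1 and 2 (numbered 13.0 and 14.0) with one mixed model for startle at baseline, acute and post-treatment, by arm and condition. Include every randomised participant with any EMG visit. Test H1 as the acute contrast and H2a as the post-treatment contrast.

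State the covariance explicitly as unstructured over visit by condition. For the three-way test, a leaner form models U minus P at the three visits with unstructured covariance. With complete data the two give the same contrast; with dropout, the difference form also relies on the U and P level adding nothing once past differences are known.

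Add a sensitivity analysis for what this model cannot repair, namely loss that follows drowsiness or adverse reactions beyond startle, or withdrawal before the acute EMG. Multiple imputation can use the KSS, recorded nine times at the acute visit, and side-effect reports as auxiliaries. Add a not-at-random variant, and say how missing startle is handled.

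Cost: plan wording and no new data. The downside is more covariance parameters from at most 80 people: 6×7/2 = 21 for visit by condition, or 3×4/2 = 6 for the difference form. The plan should name a fallback in case the larger structure does not converge; the participant random intercept alone should not be that fallback for the three-way test.

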Novel preclinical research indicates that the hypocretin/orexin (ORX) hypothalamic neuropeptide system plays a pivotal role in alcohol abuse. In rodents, antagonism of ORX receptors prevents alcohol-seeking behavior and binge-like alcohol drinking, while preserving motivation for natural rewards¹⁹⁻²². ORX receptor antagonism also robustly reduces behavioral and psychophysiological stress reactivity to threat and pharmacological challenge²³⁻²⁴. ORX antagonism may therefore be an effective strategy for disrupting the negative reinforcement cycle of addiction. Remarkably, using a within-subjects, placebo-controlled design our prelim data indicates an acute dose of suvorexant (SUV) – an FDA-approved dual ORX receptor antagonist for insomnia – robustly reduces behavioral reactivity to U-threat in adults, while sparing changes in other psychophysiological markers of threat sensitivity less relevant to AUD. ORX antagonism selectively engages the U-threat target, providing compelling evidence it is a promising pharmacological treatment for individuals with AUD and high U-threat reactivity, who frequently engage in stress-related alcohol use^{22, 25-28}.

No prior study has measured stress-related ORX target engagement in humans to uncover how ORX antagonism can be leveraged to treat AUD. The overarching goal of the current study is to advance ORX translation to the AUD clinic using a proof-of-concept

double-blind, between-subjects, randomized clinical trial design with repeat lab assessment.

All subjects will complete three lab visits of psychophysiological data collection. A subset of 20 subjects per arm (40 total) will also complete our stress task during simultaneous startle and functional magnetic resonance imaging (fMRI), pre- and posttreatment. This design allows us to address if, how, and for whom ORX antagonism modifies brain-behavior stress targets to inform and power future large scale mechanistic clinical trials.

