3.0 Objectives/Aims

Aim 1. Does an acute dose of suvorexant decrease reactivity to U-threat? H1: Relative to placebo, SUV will acutely dampen psychophysiological reactivity to U-threat, but not P-threat.

Aim 2. Does daily use of suvorexant decrease reactivity to U-threat? H2a: 4-weeks of SUV will result in greater reductions in psychophysiological reactivity to U-threat compared with placebo, and these changes will be specific to U-threat. **H2b:** SUV-related change in U-threat reactivity will be greatest amongst those with higher baseline U-threat reactivity. Exploratory: Daily SUV will similarly result in decreases in aINS and dACC reactivity and connectivity during U-threat relative to placebo, and brain change will correlate with startle change.

Aim 3. Does daily use of suvorexant change alcohol behavior, and is this change linked to brain-behavior U-threat change? H3a: Daily SUV will result in greater reductions in proportion of heavy drinking days (PHDD) and drinks per drinking day (DPDD). **H3b:** SUV-related changes in PHDD and DPDD will be greatest in those with higher U-threat reactivity. **H3c:** In all subjects, changes in alcohol behavior will correlate with changes in brain-behavioral U-threat reactivity.

Study duration. Participants will complete a Screening Session and three to five in-person laboratory sessions (dependent upon randomization) over the course of 1.5 – 2 months.

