15.0 Aim 3. Does daily use of SUV change alcohol behavior, and is this change linked to brain-behavior U-threat change? Hypothesis 3a: Daily SUV will result in greater reductions in PHDD and DPDD compared with PBO. **Hypothesis 3b:** SUV-related changes in PHDD and DPDD will be greatest in those with higher U-threat reactivity. **Hypothesis 3c:** In all subjects, changes in brain-behavioral U-threat reactivity will correlate with changes in drinking behavior. For H3a, linear mixed models will be used to assess the impact of treatment arm (SUV vs. PBO) on changes in drinking behavior over the 4-week follow-up period (daily reports). If the assumptions of linear models are violated due to skewed residual errors, we will explore the use of Poisson and negative binomial generalized linear mixed models to model drinking behavior. For H3b, baseline startle potentiation to U-threat (and in secondary models, aINS, dACC, and BNST parameter estimates) will be entered as a covariate/predictor and we will test for a baseline startle to U-threat by treatment arm interaction on drinking behavior outcomes. Lastly, the hypothesis for H3c will be tested using a linear mixed model that includes magnitude of U-threat and P-threat reactivity (startle and brain, separate models), time, and treatment arm as predictors and PHDD and DPDD as the outcomes. We expect a startle by time interaction such that regardless of treatment arm, a change in U-threat reactivity will correspond to a change in drinking behavior.

Sample Size. Our key hypothesis testing involves treatment arm by session interactions on startle eyeblink potentiation. Assuming a medium to large effect size, which is supported by our preliminary data, a sample size of 40 individuals per treatment group would conservatively yield 91% power (a total sample size of 80 individuals). To account for potential screen-fails, participants requesting to drop out of the study, and the PI withdrawing participants due to meeting termination criteria, approval for 120 participants is requested.

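### The exploratory brain–startle change correlation names no treatment-arm term; if pooled over arms, it would partly restate the two drug effects

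*Combined protocol and SAP*

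**What the plan says.** Section 3.0 (Objectives/Aims) adds an exploratory prediction to Aim 2: daily SUV will lower anterior insula and dorsal anterior cingulate reactivity and connectivity relative to placebo, and "brain change will correlate with startle change". H2a, in the same aim, predicts a larger fall in startle to uncertain threat on SUV than on placebo.

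Under Statistical Considerations, the Aim 2 text (numbered 14.0) handles the brain outcomes themselves with a model that contains arm: "fMRI variables will be tested as dependent variables in the model used for H2a". The link between the two changes then gets a single sentence: "Magnitude of brain change will be directly correlated with magnitude of startle change". There is no arm term, no partial correlation, no within-arm analysis, and no statement of which participants are combined.

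The participants with both measures are described in Section 2.0: "A subset of 20 subjects per arm (40 total) will also complete our stress task".

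For H3c (numbered 15.0), which also relates one change to another, the model lists threat reactivity, "time, and treatment arm as predictors and PHDD and DPDD as the outcomes".

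The Sample Size paragraph concerns the arm-by-session interaction on startle. It gives no figure for the brain measures or for this correlation.

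**The concern.** Two different statements can lie behind a positive brain–startle correlation. One is that the drug shifted the average of both measures. The other is that, among people on the same treatment, those whose startle fell more also had a larger fall in brain response. The arm comparisons on startle and on the fMRI variables already test the first. Only the second is new information.

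A correlation pooled over arms mixes the two. If SUV lowers both measures, the SUV participants lie low on both change scores and the placebo participants lie high on both. The cloud of 40 points then slopes upward even if there is no slope within either arm.

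At stake is how the result will be read. A significant pooled correlation would easily be taken to mean that brain change tracks startle change from person to person. The Project Summary says the findings will be used to design and power a larger mechanistic trial, so that reading could be carried forward.

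**Working it through.** **Inputs from the documents**
- 20 per arm with both measures, 1:1 (Section 2.0).
- Effect size: "Assuming a medium to large effect size, which is supported by our preliminary data", with no number, and stated for startle only.
- Power: "a sample size of 40 individuals per treatment group would conservatively yield 91% power".

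**Assumptions (not in the documents)**
- Two-sided 5% tests; bivariate normal change scores.
- Drug effect d, in within-arm SD units of the change score, between 0.5 and 0.8, applied to startle and to brain.
- Correlation of zero within each arm.
- For data loss to motion exclusion, 16 per arm as an alternative, since no exclusion rate is given.

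**Step 1: the plan's own figure.** Neither alpha, sidedness nor d is stated, so 91% cannot be reproduced from stated inputs alone. Solving for d with 40 per arm, two-sided 5%:

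d = (1.960 + 1.341) × √(2/40) = 3.301 × 0.2236 = 0.74.

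One-sided, d = (1.645 + 1.341) × 0.2236 = 0.67. Both lie within a medium-to-large range of 0.5 to 0.8. At the ends of that range, two-sided power is 61% and 95%. So 0.74 is a reasonable reference value for startle. Nothing comparable exists for the brain measures.

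**Step 2: induced correlation.** With 1:1 allocation the arm indicator has variance 1/4. With no within-arm link, the covariance of the two changes is d₁d₂/4 and their variances are 1 + d₁²/4 and 1 + d₂²/4. Hence

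r = (d₁d₂/4) / √[(1 + d₁²/4)(1 + d₂²/4)], which for equal effects is (d²/4)/(1 + d²/4).

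- d = 0.5: 0.0625/1.0625 = 0.06
- d = 0.65: 0.1056/1.1056 = 0.10
- d = 0.74: 0.1369/1.1369 = 0.12
- d = 0.8: 0.16/1.16 = 0.14

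**Step 3: rejection rate when the within-arm correlation is zero.** 100,000 simulated trials per row. The pooled Pearson test has n − 2 = 38 df and the arm-adjusted partial correlation has n − 3 = 37 df at 20 per arm.

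| d startle / d brain | Pooled, 20 per arm | Adjusted, 20 per arm | Pooled, 16 per arm |
|---|---|---|---|
| 0 / 0 | 5.0% | 4.9% | 5.1% |
| 0.74 / 0 | 4.9% | 5.0% | 5.0% |
| 0.74 / 0.5 | 8.2% | 5.0% | 7.5% |
| 0.5 / 0.5 | 6.5% | 5.0% | 6.2% |
| 0.65 / 0.65 | 9.0% | 5.1% | 8.1% |
| 0.74 / 0.74 | 11.6% | 5.1% | 9.9% |
| 0.8 / 0.8 | 13.7% | 5.2% | 11.8% |

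Inflation appears only when both measures shift. Adjusting for arm keeps the rate at about 5% throughout.

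**Step 4: what adjustment costs in power.** With a true within-arm correlation of 0.4 (assumed) and no drug effect, power at 20 per arm is 73.9% pooled and 72.8% adjusted, a loss of about one percentage point.

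**The case against.** **Pooling is not stated.** A reader might infer that the plan prescribes an unadjusted correlation over both arms. It does not say so: it leaves pooling and adjustment open. A plain pooled correlation is the most natural reading of the sentence, but the defect that can be shown is missing specification.

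**The pooled correlation is not wrong in itself.** If SUV lowers both measures, the two changes really are correlated across all participants, and finding this is no error against a marginal hypothesis. The plan never claims a within-arm link for this analysis. This objection stands. The rejection rates above apply only to the within-arm null, and it is why the pooled value should be kept as a description.

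**The analysis is exploratory.** Both Section 3.0 and the Aim 2 text label it so, and no power statement rests on it. A reader might treat this correlation as the trial's evidence that startle and brain responses share a mechanism. The documents assign it no such role.

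**Larger inflation needs larger effects.** At d = 1.0 on both measures the pooled test would reject 24% of the time. That is beyond the plan's medium-to-large description and above the 0.74 compatible with 91% power, so it should not be quoted as the size of the problem.

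**H3c is weak support.** It is tempting to say that the plan already makes this adjustment there. H3c lists arm as a predictor but names no arm-by-time term, and an arm main effect alone does not absorb a drug effect on change. The contrast shows only that arm was considered in one place and not mentioned in the other.

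**Bonferroni does not answer the point.** Section 10.0 promises such corrections in general terms. They address the number of tests, not a shift in both measures caused by arm.

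**Conclusion.** The point holds as a gap in specification with a moderate, conditional consequence. The sentence names no arm term. Read as a plain correlation over 20 + 20 participants, it would partly restate the two arm effects that the plan itself predicts. For assumed equal effects of 0.5 to 0.8 SD on both change scores, the induced correlation is about 0.06 to 0.14 and the two-sided 5% test rejects about 6.5% to 14% of the time against the within-arm null. With 16 evaluable per arm the range is about 6% to 12%. With an effect on only one measure there is no inflation.

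These figures rest on assumed values of d, normality, and a two-sided 5% level; the documents supply none of them for this analysis. The documents do not support saying that the plan commits to an unadjusted pooled test, or that any primary or confirmatory error rate is affected. The change is worth making because it is cheap and removes an ambiguity in how the result would be read.

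**What to change.** Replace the sentence under Aim 2 with:

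> *The association of brain change with startle change will be estimated with treatment arm in the model (partial correlation adjusted for arm); the pooled unadjusted correlation will be shown descriptively.*

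Apply the same wording to each region and to the activation and connectivity measures.

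An arm-by-startle-change term may be added to show whether the association differs between arms. It is optional: it uses a second degree of freedom and would be imprecise with 20 per arm.

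Cost: one sentence and one degree of freedom (37 instead of 38 at full enrolment). No new data, visits or participants are needed.
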